For purposes of this study, the Neurotech Vital Compact is to be used per the Instructions for Use (IFU) provided in Appendix XI. A Vital Compact Quick Start Guide is also included in Appendix XI.

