8.10.1 Device Training

Subjects will be briefed by the designated non-blinded site personnel on the set-up of the Neurotech Vital Compact device or the itouch Sure Pelvic Floor Exerciser (in accordance with the allocated treatment as per the randomisation schedule). Subjects will then be asked to follow

the set-up instructions and complete a 30 minute session with the Neurotech Vital Compact device or a 20 minute sessions with the itouch Sure Pelvic Floor Exerciser in accordance with the appropriate Instructions for Use. Subjects will be at liberty to alter the intensity of the stimulation to the highest tolerable level and will be advised on the importance of achieving a strong pelvic floor contraction. Guidance will be given on the typical minimum intensity setting to achieve this effect. Subjects will be advised that it not necessary to achieve this level in their first session but that they should gradually increase the setting in their first week of use.

All of the subject's training will be documented. Subjects unable to demonstrate competent use of the Neurotech Vital Compact device or the itouch Sure Pelvic Floor Exerciser will be withdrawn from the clinical study.

The subject will be provided with the Neurotech Vital Compact device or the itouch Sure Pelvic Floor Exerciser to take home with them. Details of all devices provided, including the serial/lot numbers, will be recorded.

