- Stimulation should not be applied over the carotid sinus nerves, particularly in patients with a known sensitivity to the carotid sinus reflex.
- Although compliant with applicable EMC requirements, this device may still interfere with more sensitive equipment, please move away or switch off this device if necessary.
- Specific patient groups (e.g. the elderly) may require further attention and care.
- Before using the equipment, a visual inspection must be performed (check for a broken enclosure, damaged connector or exposed wires). If there is any doubt, the equipment must not be used.
- Once the treatment has ceased, always remember to switch off the controller.
- If in doubt, always seek medical advice.
- Medical advice must be obtained before use on persons who are insulin dependent diabetics or for persons who are under medical supervision for any cognitive dysfunction.
- When repositioning electrodes during treatment, always pause or stop the controller first.
- Simultaneous connection of a patient to high frequency surgical equipment may result in burns at the site of the stimulator electrodes and possible damage to the stimulator.
- This device can deliver current densities in excess of 2mA/cm^2 when used at a high intensity with small electrodes.
- Do not use the device with the electrodes positioned on injection sites (of medications/drugs), such as hormone treatment sites.
- Do not touch the electrodes, connectors or lead pins with your fingers while the stimulation session is in progress. Always pause or switch off the controller before handling the electrodes.
- The device must not be used with any other unit which delivers electrical current to the body (e.g. interferential or another muscle stimulator).
- It is advised that the patient use the bathroom before starting each treatment session.
- Always check the product leads before use and do not use if they are damaged in any way.

Adverse Reactions:

- A small number of isolated skin reactions have been reported by people using muscle stimulation devices, including allergies, a prolonged reddening of the skin and acne.
- On very rare occasions, first-time users of NMES have reported feeling light-headed or faint. In this event, we recommend that the patient switches off the unit and sits down until they are feeling better. They may then resume the treatment.
- Patients should stop using the device and should consult their clinician if they experience adverse reactions from the device.

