Notes:

- The patient should only run one full treatment session per day to reduce the potential for muscle fatigue. A treatment session is defined as 30 minutes of treatment, even if this is broken down into shorter 10- or 15-minute sessions. This restriction may be changed depending on the prescribing clinician.
- An effective treatment should not cause undue discomfort.

Important:

- The safety information provided in this User Manual must be followed.
- The unit should only be set-up and operated according to the instructions laid-out in this manual.
- The patient should always cease using the unit and consult their doctor if they are feeling light headed or faint.
- **neurotech®** will not accept responsibility if the guidelines and instructions supplied with this unit are not followed.

IMPORTANT

- **NEVER** connect leads or wires from other equipment such as computers, games, cameras etc. to the controller.
- **NEVER** connect the leads provided with Vital Compact to any other equipment.
- If in doubt, contact **neurotech®**.

CARING FOR YOUR NEUROTECH VITAL™ ELECTRODES

IMPORTANT ELECTRODE INFORMATION

In order to prolong the life of the electrodes, after every few treatment sessions, the patient should sprinkle a few drops of clean water over the adhesive surface of each electrode with their fingertips and then gently rub it over the complete surface of the electrode. This will clean away debris and help to rehydrate the adhesive surface.

Note: This should only be done with the side of the electrode which adheres to the skin. The side of the stress electrode which adheres to the garments should be left affixed to the garment.

- The electrodes are for single person use only.
- You should always ensure your skin is clean and free from oils, creams and other lotions before use.
- The durability and effectiveness of the electrodes depends entirely on the proper use, storage and care on the part of the user, certain skin types and the type, duration, number of sessions, intensity used and site of stimulation.
- Ensure your hands are clean before handling electrodes. You should avoid touching the skin-side of the electrodes with your fingers as much as possible when applying or removing the garments or electrodes, as this can transfer oils and skin particles to the electrodes' surface.
- After use, replace the liners on the adhesive side of the electrodes and store your unit in a cool, dry place until the next use.

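### The Vital Compact manual gives two different instructions for a woman who feels light-headed or faint: resume once better, or always stop and consult

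*Protocol*

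**What the plan says.** Protocol section 7.1.1 makes the manual the operating instruction for the trial: "For purposes of this study, the Neurotech Vital Compact is to be used per the Instructions for Use (IFU) provided in Appendix XI". The Assistance text at the end of the manual says that it was written for this study.

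Three statements in Appendix XI bear on light-headedness.

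- Adverse Reactions, faintness bullet. It opens "On very rare occasions, first-time users of NMES have reported feeling light-headed or faint" and continues "we recommend that the patient switches off the unit and sits down until they are feeling better. They may then resume the treatment".
- Adverse Reactions, next bullet: "Patients should stop using the device and should consult their clinician if they experience adverse reactions from the device".
- Important list: "The patient should always cease using the unit and consult their doctor if they are feeling light headed or faint". The same list states: "The safety information provided in this User Manual must be followed".

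In the protocol body, section 9.2 lists light-headedness among the anticipated events of neuromuscular stimulation, calls it very rare, and advises having a seat close by. Section 7.8 makes stopping the device the first response to any suspected device-related event. Under section 8.10.1 each Vital Compact subject is to "complete a 30 minute session with the Neurotech Vital Compact device" at the baseline visit, after a briefing by unblinded staff. The same section says of later use that "they should gradually increase the setting in their first week of use".

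**The concern.** A first-time user who feels faint falls under both the permissive sentence and the strict one. The first lets her restart when she feels better, with no contact with anyone. The second tells her always to stop and consult. The manual does not say which prevails, and it says that all of its safety information is to be followed.

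The manual also does not define a first-time user. A woman still new to stimulation during her first week at home could take the permissive sentence as meant for her. That is an inference about how the text might be read; no section says it.

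What is at stake is consistent handling of a listed anticipated event during unsupervised home use. There is a smaller reporting side: the permissive bullet gives no prompt to tell the clinic, although other parts of the protocol do collect adverse events.

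**Working it through.** No arithmetic applies. The documents give no rate for light-headedness beyond calling it very rare, so no expected number of events can be calculated. The check is a comparison of the texts.

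| Question | Faintness bullet (Adverse Reactions) | Next bullet (Adverse Reactions) | Important list |
|---|---|---|---|
| Who is covered? | First-time users of neuromuscular stimulation | Patients with adverse reactions from the device | The patient, without limit |
| First action? | Switch off and sit | Stop using | Cease using |
| Consult a doctor or clinician? | Not mentioned | Yes | Yes |
| Restart on own judgement? | Yes, once she feels better | No such permission | No such permission |

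1. **Overlap.** The Important list uses the word always and makes no exception, so first-time users are included. The faintness bullet sits in a list of adverse reactions, so the general bullet that follows it also applies. A first-time user is therefore under all three texts.
2. **Agreement.** All three start with stopping, and so does protocol section 7.8.
3. **Disagreement.** Two questions get different answers: whether a doctor or clinician must be consulted, and whether the woman may restart by herself. If ceasing is read as a temporary stop, the second difference narrows, but the requirement to consult still separates the texts.
4. **Force.** The faintness bullet is a recommendation followed by a permission. The other two are directions. Section 7.1.1 and the statement that the safety information must be followed bring all of them into the trial.
5. **Safeguards already present.** The first session is in clinic (section 8.10.1). Women may telephone the clinic whenever they have a concern (section 8.10.4) and are called at Week 1, when adverse events are asked about (section 8.11.2). The manual's running instructions recommend standing, but with the hands on something fixed such as a table, and they let women who cannot stand for the full session lie down or split it. The Quick Start Guide offers standing, reclining or lying. Section 9.2 advises a seat close by.

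Steps 1 and 3 establish the inconsistency. Steps 2 and 5 keep it small.

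**The case against.** The strongest reply is that the texts can be reconciled. The faintness bullet only permits; the Important list directs. A woman who stops and consults breaches neither, so following the stricter text satisfies the whole manual. The manual also tells users to seek medical advice when in doubt. The permission is limited to first-time users, and the first use is supervised.

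Much of this stands, and it is why the point is minor. It does not remove the inconsistency. A woman who relies on the permission and restarts has done what one sentence allows and has not done what another requires. Reconciling the two depends on her finding the stricter text and treating it as overriding.

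Some stronger inferences are tempting and should not be drawn.

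- *A material fall risk at home.* A reader might combine standing treatment with the first-week increase in intensity. The documents do not link faintness to intensity, and they provide hand support, reclining or lying positions and a nearby seat.
- *A dose cost in percentages.* Against the 60 prescribed sessions in SAP section 3.7.3, one lost session would be 1/60 = 1.7% of target use. That would be a cost of stricter handling, not a measure of this problem, and the Important list already requires stopping and consulting. The schedule has two rest days a week, and the SAP counts sessions from the daily record without a minimum duration, so an interrupted session may be made up or may still count.
- *A threat to the blind that needs a new call procedure.* Section 7.8 already allows the investigator to learn the allocation from unblinded staff if necessary.

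**Conclusion.** The manual is inconsistent as written, and the correction is worth making. The size is minor: one sentence, one arm, and an event described as very rare. There is no effect on the primary endpoint, the sample size, power or type I error.

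A reader might also infer that light-headedness will be under-reported in the Vital Compact arm and the safety comparison distorted. The documents do not support that. The faintness bullet lacks a prompt to report, but the Week 1 call and every visit ask about adverse events, and no event rate is given from which a shortfall could be estimated.

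The conclusion rests on two readings: that always in the Important list includes first-time users, and that feeling light-headed or faint means the same thing in both lists. Both are the plain meaning of the words.

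**What to change.** Put one rule in both the faintness bullet under Adverse Reactions and the Important list, for example: *Switch off the unit, sit or lie down, and contact your study doctor; do not resume treatment until the study doctor advises it.* Changing only the faintness bullet would leave the two lists naming different contacts, and the Important list with no rule on restarting. Naming the study doctor agrees with the manual's Assistance text, which already sends device problems there. The general stop-and-consult bullet does not conflict with this rule and can stay.

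No new telephone procedure is needed. Women can already call the clinic, and section 7.8 covers the case in which the doctor has to know the allocation.

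The cost is a short revision of a manual that was produced for this study, with IRB notification. An occasional session may be missed or delayed while advice is sought, which the Important list already implies. No visits, assessments or analyses change.

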14.12 Appendix XII. itouch Sure Pelvic Floor Exerciser Instructions for Use

Instructions for Use

itouchsure

PELVIC FLOOR EXERCISER

IMPORTANT: Read this manual carefully before starting to use your itouch sure Pelvic Floor Exerciser. INAPPROPRIATE OR INCORRECT USE COULD BE UNSAFE.

This user manual is provided to you as part of your participation in a clinical study. Please only use the iTouch sure as directed by your study doctor

Caution: U.S. Federal Law restricts this device to sale by or on the order of a licensed healthcare practitioner.

Support

Please call your study doctor if you have any questions.

TABLE OF CONTENTS

CONTENTS OF PACKAGE	3
Before you use itouch sure for the first time	3
CONTRAINDICATIONS, WARNINGS AND PRECAUTIONS	4
ITOUSH SURE INDICATIONS FOR USE	5
TREATING URINARY INCONTINENCE	6
HOW TO SET UP AND USE itouch sure	7
ITOUSH SURE "SMART FEATURES"	9
ITOUSH SURECONTROLS	11
SCREEN DISPLAYS	14
Treatment	16
BATTERY USE	17
ITouch SURE CLEANING AND STORAGE	18
TROUBLESHOOTING	19
PRODUCT SPECIFICATIONS	19
PROGRAM SETTINGS	20

CONTENTS OF PACKAGE

Itouch Sure Control Unit
itouch sure Electrode
Connecting lead wire
Four AA batteries
Instruction booklet
Storage pouch

Before you use itouch sure for the first time

An examination of the vaginal tissue should be completed prior to initial treatment to rule out any contraindications, establish the baseline tissue condition and assess the physiology discussed below. Pelvic floor stimulation may not be successful if the urethra has excessive scarring or if there is significant denervation of the pelvic floor. The neuromuscular structures involved in urine storage must also be at least partially preserved. Patients with intact sacral reflex arcs and some innervation of the pelvic floor may benefit from pelvic floor stimulation.

The itouch sure unit must only be used in accordance with the advice of your treating physician. Be sure to read the instructions included in this booklet to supplement the information provided to you by your physician.

CONTRAINdications, WARNINGS AND PRECAUTIONS

Contraindications

Should not be used if you have any of the following conditions:

If you have a heart pacemaker or a rhythm problem

If you are pregnant or trying to become pregnant

If you have been diagnosed or treated for cervical, or any pelvic, cancer

If you have, or have had epilepsy

While driving, or during any activity in which involuntary muscle contractions may put the user at undue risk of injury

If you have:

An active urinary tract infection

Recent history of vaginal bleeding between menstrual periods

Infections or lesions in the area of electrode placement

Diminished sensory perception

Inability to understand the directions of use or operate the device correctly

History of urinary retention or post-void residual volume greater than 200 cc If any discomfort occurs when inserting the electrode consult your study doctor.

Warnings

The patient should discontinue use and immediately consult the clinician if irritation, pain or unusual bleeding occurs.

Keep out of reach of children.

Do not use in water (for example, while bathing) or device may shock user.

This equipment is not rated for use while immersed or under dripping water.

Do not use simultaneously with high frequency hospital diagnostic/therapeutic equipment. Doing so may result in burns at the site of the electrodes and possible damage to the device.

Do not use simultaneously with patient monitoring equipment such as EKG monitors without investigating the possibility of output from the device causing erroneous monitor readings.

Do not carry batteries in a pocket, purse or other place where the terminals could become short circuited, (e.g. by way of a coin or paperclip). Intense heat could be generated and injury may result.

The long term effects of chronic electrical stimulation are unknown.
Do not use with products other than those recommended by your treating clinician.

Precautions

Review the following precautions before using:

It is not recommended to use the device while under the influence of alcohol or other substances, such as sleeping pills or tranquilizers, which could affect the patient's ability to operate the system correctly.

Removing or inserting the electrode while the system is on could result in discomfort.

Use while operating hazardous equipment, machinery or motorized vehicles could cause abrupt changes in stimulation which can startle the patient and create a hazard.

Do not use in close proximity (e.g. <3ft.) to transmitting cellular (wireless) telephones or two-way radios. This equipment may produce instability in the stimulatory output. Sudden unexpected changes in output could startle the patient and create a hazard.

Use while sleeping is not recommended.

The patient should discontinue use and consult a clinician if a significant change in the stimulation sensation occurs without changing the intensity settings. It is normal to feel a difference in sensation when changing positions during stimulation.

Caution should be used following recent surgical procedures when muscle contraction may disrupt the healing process.

ITOUCH SURE INDICATIONS FOR USE

Your physician has prescribed the use of the itouch sure Pelvic Floor Exerciser for the treatment of your urinary incontinence symptoms. itouch sure is indicated for the rehabilitation and strengthening of weak pelvic floor muscles in the treatment of stress, urge, and mixed urinary incontinence.

TREATING URINARY INCONTINENCE

You have been selected for this study because you suffer from Stress Urinary Incontinence and the iTouch sure is indicated for the treatment of this condition. The device may also be used for other forms of incontinence however in this study you will only be using the Stress treatment.

Please always ensure that the letters “STRES” are displayed at the top of the screen during treatment. If the words URGE, MIXD or TONE are displayed then you are using the wrong program. Press button P until STES appears on the screen and continue treatment

Please follow the instructions for use given to you by your study physician. The initial electrode fitting and the treatment session should be done under medical supervision by study staff.

You should experience the sensation of a muscular contraction in the vagina when using itouch sure.

HOW TO SET UP AND USE itouch sure

Setting up and using the itouch sure Pelvic Floor Exerciser is very simple.

Step 1: Before you use itouch sure for the first time, clean the Probe gently with soap and water (do not immerse).

Step 2: Insert two AA batteries into the Control Unit (see "Inserting the Batteries"). To test that the batteries have been inserted correctly and that the unit is working, press and hold the "ON" button for three seconds. The screen will light up and you will hear a beep.

Step 3: Insert the two prongs of the lead wire into the matching receptacle end of the itouch sure Probe wire.

Step 4: Plug the USB port end of the lead wire directly into the bottom of the itouch sure Control Unit as shown.

Step 5: Before you insert the itouch sure Electrode, empty your bladder (urinate), and **make sure the itouch sure Control Unit is switched OFF.**

Step 6: Lubricate the itouch sure Probe with the conductive gel provided.

Step 7: After the wires are securely connected, insert the Probe into the vagina, in the same way you would a tampon, until only the flange at the end is visible.
The Probe will naturally position itself with the widest part of the flange vertically (see diagram).

Note: The flange should not be inserted into the vagina and should remain outside of the vagina at all times.

It is important to relax and choose a comfortable position - such as a semi-reclined pose - or to lie down on a bed or couch when performing this step.

Step 8: Turn the itouch sure ON by pressing the ON button (↑) for three seconds. When the unit is switched ON an audible "beep" will be heard.

Step 9: You will be using the STRES program in this study. The P Button is used to change the program. Please do not change the Program. If you accidentally change it you can get the STRES program back again by pressing the P button a few times.

Step 10: After insertion, adjust the strength by pressing the strength (↗) button. The selected intensity will appear on the display. Begin to increase the strength to a level where you feel the sensation but is not overly painful. You may not feel any sensation until the strength reaches a certain level. This level may vary based on individual use and any pre-existing physical conditions, but stimulation occurs as soon as the strength is registered above 0.

Note: It is important to be conservative upon initial use. As long as you can feel the contraction, itouch sure is working. You can build up the strength slowly over a number of days.

During use you may feel cramping. If this happens, stop using the itouch sure until the cramping goes away, then start again using a lower strength.

Step 11: To decrease intensity, press the strength down (▼) button.

NOTE: itouch sure cycles between active stimulation and periods of rest to allow your muscles to recover between contractions. It is normal to feel the stimulation ramp down, stop briefly, and then ramp back up again during treatment. (During the "rest" period, the strength display flashes "0.0".)

Step 12: The length of each session has been set at 20 minutes. Please do not change the preset time.

Step 13: When the timer reaches zero, your session is complete. Press and release the OFF button once to turn off the power or it will automatically turn off.

Step 14: Remove the itouch sure Probe from your vagina by grasping the probe flange and gently pulling outward. It is important that you do not pull from the wires, as it may become disconnected at the two-prong connection.

Step 15: Wash and thoroughly dry the itouch sure Probe before placing it and the itouch sure Control Unit into the storage pouch.

Note: As with any new exercise regimen, with the first few sessions your muscles may be a bit sore the next day.

Note: The next time you turn on the unit, it will default to the mode last used but at half strength. Thus, it may be beneficial for you to adjust the intensity to the desired setting for your next treatment session prior to turning off the itouch sure Pelvic Floor Exerciser.

iTOUCH SURE "SMART FEATURES"

itouch sure Pelvic Floor Exerciser is designed with state-of-the art electronic features including:

Controllable Stimulation

The strength of the stimulation is under your control. You can gradually increase or decrease the intensity whenever you want to make sure the stimulation always feels comfortable.

Easy Start - One Touch Memory

The itouch sure has intelligent memory that enables the unit to remember the last settings you used, and return to similar settings at your next use.

•Automatic Safety Shutoff

This feature automatically turns the device off after 20 minutes of use to protect the pelvic floor muscles from being overworked. If your physician recommends sessions that are longer than 20 minutes, you can adjust the device to override the safety shutoff and allow a longer session.

ITOUCH SURECONTROLS

To turn iTouch Sure ON: Press and hold the ON button for three seconds.
 When the unit turns on, you will hear a beep.

Memory Start

If you turned the unit off before completing the session, it will automatically start in the program you used last, at about 50% of the strength level you were using. This way you can adjust the strength comfortably for each new session.

Strength UP (▲) Button

To increase strength: Press and hold the Strength UP button until your desired strength is displayed on the screen.
 You may not feel any initial sensation, as it is a gentle increase of intensity.
 To increase the strength, press and release the button until you reach your required level. The strength will increase in 0.5 increments up to a maximum of 99.5.

Strength DOWN (▼) Button

To decrease strength: Press and hold the Strength DOWN button until the desired strength is achieved. To decrease the strength, press and release the button until you reach your desired level.

Program (P) Button

iTouch Sure has four preset programs which appear as STRES, URGE, MIXD and TONE on the screen. You will be only using the STRES program in this study. The P Button is used to change the program. Please do not change the Program. If you accidentally change it you can get the STRES program back again by pressing the P button a few times.

Lock Button

The Lock button can be used to lock all the controls except for the strength down and OFF buttons. This way you won't accidentally change the settings while you use the unit, but you still have the ability to decrease the strength at any time. To lock the unit, press and hold down the Lock button for three seconds until LOCK is displayed on the screen. To unlock the unit, simply repeat.

(⌚) Time Selector Button

The itouch sure Pelvic Floor Exerciser counts down the minutes of your session. This countdown is displayed on the screen. When the count reaches zero, the unit will automatically turn off.

Each time you switch on the itouch sure, the time selector will be set at 20 minutes which is the treatment time for this study. Please do not change the timer setting.

To PAUSE the session - in case you need to suspend the treatment session and resume later - hold down the Time Selector button for three seconds. The display will read "PAUSE".

To return to the main screen, press any other key and you will return to the settings where you left off.

OFF (ⓧ) Button

To turn itouch sure OFF: Press the OFF button. You will hear a double beep.

NOTE: Always make sure the unit is OFF before removing the itouch sure Probe from your vagina.

SCREEN DISPLAYS

The screen lights up whenever a button is pressed.

LEADS ALARM

itouch sure monitors the contact between you, the Probe, and the itouch sure Control Unit. If either of these go outside of a standard range, while the strength is above 20.0, the unit will flash "LEADS", beep three times, and return strength to zero.

The most common causes are:

- Poor contact with your vaginal walls.
- A broken lead wire.
- A faulty connection at the USB port or at the dual probe connectors.

If the LEADS alarm sounds, make sure the wires are connected properly. If that doesn't solve the problem:

Change the position of the probe in the vagina; or

Change your body position; or

Add lubrication to the itouch sure Probe so that it can make a better contact with the vaginal tissue.

If you have taken the above steps above and the alarm still shows, please refer to Troubleshooting section for further information.

Treatment

Please follow the instructions for use given to you by your study physician. The initial electrode fitting and the treatment session should be done under medical supervision by study staff.

Set the strength level to that prescribed by your study doctor. If you experience discomfort reset the intensity down one step. Don't "overdo" it early on. As long as you can feel the contractions, itouch sure is working properly. You can build up slowly over a number of sessions.

Your muscles may be sore the next day- the same reaction you would get with any new exercise - and you may need to stop using your itouch sure for a day or two until the soreness goes away, and then start again using a lower strength and shorter treatment time. As the pelvic floor muscles get stronger, you will be able to increase your strength level and time.

[figure not shown]
NOTE: itouch sure cycles between active stimulation and periods of rest. It is normal to feel the stimulation ramp down, stop briefly and then ramp back up again during treatment.

BATTERY USE

Inserting the Batteries

Open the battery cover:

Press down in centre of battery cover and slide the cover downwards in the direction of the raised arrows.

Insert the batteries in the direction shown inside the case. Make sure that the ribbon goes behind the batteries, which makes them easier to remove later. When the batteries are running low, a low battery indicator will show on the screen (battery symbol) and the display will begin to fade. The intensity of your workout, however, will stay the same until the battery runs out and the unit shuts off.

Battery removal and replacement:

When the batteries need to be changed the low battery sign, " BATT", will be displayed on the screen. To remove batteries, pull gently on the ribbon behind them. Remove batteries from your itouch sure unit if the unit is unlikely to be used for a long period.

Battery type:

ONLY use either AA alkaline batteries. . DO NOT mix batteries of different types. Do not try to recharge alkaline batteries. Properly dispose of used batteries, as batteries should not be disposed of with household waste.

Warning:

Keep batteries out of the reach of small children

If battery leakage occurs and comes in contact with the skin or eyes, wash thoroughly with lots of water.

Do not attempt to revive alkaline batteries by heating, charging or other means

Never put batteries in a fire nor try to disassemble them

ITouch SURE CLEANING AND STORAGE

Cleaning the Probe

It is important to clean the itouch sure Probe after each use to prevent bacterial growth that could possibly lead to an increased risk for infection. Wash the probe with warm soapy water and then wipe the probe with an alcohol wipe, and dry thoroughly.

DO NOT immerse the probe under water, or in boiling water, as this will damage it.

The Probe that is supplied with the itouch sure Pelvic Floor Exerciser is intended strictly for one person's use. Do not let anyone else use your itouch sure.

Cleaning the itouch sure Control Unit

Clean the itouch sure Control Unit weekly with a cloth or paper towel dampened with soapy water, but DO NOT immerse it under water. Dry it with a clean cloth and make sure it is fully dry before storing the unit in its pouch.

Storing Your itouch sure Pelvic Floor Exerciser

Store itouch sure in its pouch.

Do not store at high temperatures or in damp conditions.

Do not store or use near a microwave oven.

Remove batteries if storing for more than 30 days

TROUBLESHOOTING

If you have problems with the operation of your itouch sure Pelvic Floor Exerciser, follow these directions:

Fading display or no display -

The display will begin to fade as the batteries run low, and there will be nothing on the display when there is no power left in the batteries. Make sure the batteries are charged and inserted correctly. If necessary, replace them. (For more information, see " Battery Use" on page 19)

Controls won't work -

The unit may be on LOCK, in which case the display will read "LOCK". Hold down the Lock button on the side for three seconds. If "LOCK" is not showing on the display, remove and replace the batteries.

No sensation / No leads alarm -

If you feel no sensation when you use itouch sure, first try increasing the strength level according to instructions. If that does not work, dampen your hand with water and a little table salt. Holding

the Probe in your hand, increase the strength gradually. If you don't feel anything, the unit may need to be replaced.

NOTE: If you are able to feel the sensation in your hand but not in your vagina, you may have nerve damage. Stop using itouch sure and call your physician

PRODUCT SPECIFICATIONS

Maximum Intensity	50V zero to peak.
Setting	0·100 in steps of 0.5
OC cutout	below 160 Ohm.
Constant current	160-470 Ohm 470-2000 Ohm constant voltage.
Channels	Single
Waveform	Asymmetrical rectangular
Max Pulse energy	*Total output limited to 25uC per pulse
Power	2 xAA Alkaline
Battery life	At least 15 hours at 50mA 300uS 50Hz
Adjustable Timer	10, 20, 30 45, 60, 90 min defaults to 20 min
Pause button	"Clock" key when running
Output plug	Fully shielded: touch-proof mini USB
Weight	90 gms without batteries
Dimensions	102 x 53 x 30 mm
Safety Classification	Internal power source.
Type BF	Designed for continuous use. No special moisture protection.
Environmental Operating:	Humidity: 20% - 65% RH
Storage Humidity:	10 to 90% RH Temperature range: 0°C to 55°C
Temperature range	0°C to 35°C

[figure not shown]
The electrical specifications are nominal and subject to variation from the listed values due to normal production tolerances.

PROGRAM SETTINGS

Program	Hz	Pulse Width (μS)	Ramp Up & Down (Sec)	Plateau (Sec)	Off (Sec)	Default Program Duration (Min)
STRESS	50	300	1	5	10	20
URGE	10	200	1	5	10	20
MIXED	20	250	2	5	10	20
TONE	35	250	2	3	6	20

Device Output Parameters and Waveform

The waveform below illustrates a typical output waveform from the iTouch Sure device:

Max Pulse Energy: 23 μ C

Use special precautions regarding EMC according to the information provided below.

Other portable and mobile RF communications equipment can affect performance.
Do not use when adjacent to or stacked with other electrical equipment.

Assistance

If you have any problems with your device please contact your study doctor whose contact details are on the Informed Consent form you received at the beginning of the study. For further assistance you may contact

Expedite Research, LLC [name]
[name]
Office [name]

These instructions for use were created specifically for study BMR 13 1001 by:

Bio-Medical Research Ltd. [name]
